## 4.2.1 Escalation Model

A modified Bayesian Optimal Interval (mBOIN) design will be utilized to make recommendations at end of each DLT evaluation period (Liu, 2015). The target DLT rate is set to  $\phi = 30\%$  with the assumptions that  $\phi_1 = 0.6\phi$  is the highest sub-therapeutic DLT rate and  $\phi_2 = 1.4\phi$  is the lowest DLT rate that has excessive toxicity. Under these assumptions, the thresholds that minimizes the decision error at end of each cohort are  $\lambda_1 = 24\%$  and  $\lambda_2 = 36\%$  (Liu, 2015).

Based on the accrued data (on each dose level) the mBOIN recommendations are supplied in Table 11.

**Table 11 Modified BOIN Recommendations** 

	Total Number of DLT Evaluable Subjects Treated on a DL Cohort	3	4	5	6	7	8	9
Recommendation	Escalate	0	0	≤1	≤1	≤1	≤1	≤2
Based on Total Number of DLTs on the DL Cohort	Remain	1	1	-	2	2	2	3
	De-escalate	2	2	2	3	3	3	4
	Terminate a dose level	3	≥3	≥3	≥4	≥4	≥4	≥5

DL=dose level; DLT=dose-limiting toxicity.

Version: 4.0

The DLT rate per each period-specific dose level may be provided to the DEC (supplementary to the DLT rate of the DL cohort) when the DEC is considering the dosing sequence of the next DL cohort. The mBOIN recommendation for the period-specific dose level may be interpreted in the context of Table 11 above (modified mBOIN recommendations). For example, the DLT rate of 3 mg when administered as priming dose will be provided, as will the DLT rate of 3 mg when provided as intermediate dose.

Given the different perspectives the different DLT rate estimates provide, the DEC will evaluate all available data to recommend the doses for the next DL cohort; the Safety Committee will make the final decision. A template for DLT reporting is provided in Appendix 9, Table 29.

#### 4.2.1.1 Modifications to BOIN

The BOIN has the following general stopping rules:

- i. Escalation stops if 80 subjects have already been dosed.
- ii. Escalation stops if there are 9 subjects already treated on a DL cohort proposed by the DEC.

### Dose Level Termination:

A potential drawback of the basic BOIN design is that, theoretically, a "very toxic" DL cohort could be investigated in multiple cohorts, if a neighboring DL cohort is not toxic. To avoid this problem, a dose level termination criterion is implemented (for DL cohorts with at least 3 DLT evaluable subjects): A DL cohort can no longer be investigated if an additional DLT-free cohort would lead to de-escalation.

### Cohort Size:

In the standard titration part, it is allowed to estimate the DLT rate for the DL cohort if 1 subject is non-DLT evaluable and the remaining 2 subjects are DLT-evaluable, provided that neither of the 2 subjects experienced any grade ≥2 AE within the first 7 days of Cycle 1, or any DLT during the 21-day DLT period. (If a dose level has in total 2 subjects being DLT-evaluable and no DLTs are observed, the BOIN rule is to escalate.)

Also, over-recruitment by 1 subject is allowed, so that each 3-subject cohort may consist of 2 to 4 subjects who are evaluable for DLT.

It is noted that for 5 DLT evaluable subjects, the possibility to "remain" cannot be concluded. (The estimate DLT rate is 0%, 20%, 40%, 60%, 80% or 100%. No estimate within the limit of "remain": [24%, 36%].) In this case, the number of DLT evaluable subjects is brought up to 6 by an additional subject to regain this option.

In case a cohort had less than 3 DLT evaluable subjects, the next DL cohort (on the same dosing sequence) may be enlarged to bring the number of subjects on the dose level up to a multiple of 3.

## Parallel Cohort(s) for Clinical Confirmation:

To better understand the safety, tolerability, PK, pharmacodynamics or anti-tumor activity, up to 7 additional subjects (ie, maximum total DL cohort size n=10) may be allocated in parallel to full-dose levels that are considered safe for such allocation (dose levels at or below the currently investigated full dose). In addition, new priming and/or intermediate dose levels may be investigated in a parallel cohort, provided its full-dose level does not exceed the most recent safety-cleared full-dose level. Any DLTs observed in a parallel DL cohort will be presented to the

Version: 4.0

DEC, and it will be up to the DEC to determine how these would impact the determination of the dose levels in the next cohort.

# 4.2.1.2 Describing Grade ≥2 CRS Occurring During the First 7 Days of Cycle 1

The incidence of grade  $\geq 2$  CRS occurring during priming dose will be supplemented to the DEC as descriptive statistics to determine the feasibility of the priming dose level from a CRS management perspective. The CRS event will only be used in the mBOIN model if it is a grade  $\geq 3$  CRS.

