If any single-subject DL cohort is expanded to a total of 3 subjects (based on the trigger point above being reached), all subsequent DL cohorts will initially have 3 subjects per cohort.

Version: 4.0

The next DL cohort, possibly including a higher full-dose level, can start only once the DLT period for the previous DL cohort has been assessed and the next full-dose level is proposed by the DEC and endorsed by the SC. Parallel cohorts may be initiated at any time, provided the full-dose level of the parallel cohort has already been safety-cleared by the SC and does not equal or surpass the full-dose level in the DL cohort under investigation. The DEC will recommend the full-dose level for the next cohort of subjects, including whether 1 or 2 intermediate doses should be given, to the SC and this will need to be endorsed by the SC prior to using the recommended or higher full-dose in the next cohort dose level implementation. The descriptive DLT tables provided to the DEC (see Appendix 9) will provide an overview of the DLT rates considering the whole DL cohort (as intended in the original protocol), and considering the individual period-specific dose level.

For any DL cohort that enrolls more than 1 subject, there will be a minimum of 24 hours between an individual subject's treatment infusion stop and a subsequent subject's treatment start in the same cohort, to account for any acute safety signals in each new dose level. The 24-hour treatment window between same-cohort subjects will not apply to backfilling cohorts enrolling subjects to be exposed to previously safety-cleared full dose levels.

An overnight stay (24 hours in-hospital observation) will be required for all subjects after administration of GEN1044 on Day 1 and Day 8 during Cycle 1 only and may be required for additional subjects and/or dose levels if recommended by the sponsor SC. If a second intermediate dose is implemented at C1D15, the sponsor may decide to require additional 24-hour hospitalization following this dose administration.

During treatment in the Dose Escalation part, safety assessments will be performed as indicated on Table 1. For the assessments of each cohort, the dose-limiting toxicities (DLTs) will be collected for the first treatment cycle, ie, a DLT evaluation period of 21 days from the priming dose (or 28 days if two intermediate doses are applied).

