#### 11.1.7 Dose-Determining Analysis Set – Dose Escalation Part

The dose-determining set (DDS), which is used to define the number of DLT evaluable subjects on a DL cohort, will include all FAS subjects in the escalation part who meet the exposure criterion (defined below) and have sufficient safety evaluations, or experience a DLT prior to the 2nd full dose administration. The DLT period will extend until 7 days after the first full dose (see Section 4.2).

A subject meets the exposure criterion if all doses, up to and including the 1st full dose, are administered in a timely fashion: In general, the individual doses should not be delayed more than 7 days. However, longer dose delays might be acceptable if the DEC considers the assessments still to be appropriate. The first full dose should be administered at latest by 30 calendar days after C1D1 (if one intermediate dose is administered), or by 38 calendar days after C1D1 (if two intermediate doses are administered), counting the day of first exposure as C1D1.

If there is a longer dose delay the subject is considered as non-DLT evaluable (as long as the reason for the dose delay, or the dose delay itself, is not classified as a DLT). DLTs occurring beyond the DLT period will be presented, but not contribute to the DLT rates for the DL cohort per mBOIN.

Subjects who do not experience a DLT will be considered to have sufficient safety evaluations if they have been observed for  $\ge 21$  days (or  $\ge 28$  days if 2 intermediate doses are applied) following the priming dose, and are considered by both the sponsor and investigators to have enough safety data to conclude that a DLT did not occur.

For a period-specific dose level (doses up to and including 1st full dose), a subject is considered as DLT evaluable if the dose was timely administered (ie, not delayed for more than 7 days) and had sufficient safety evaluations up to the subsequent dose administration to conclude if a DLT did occur or not. The relative DLT periods for priming and intermediate doses extend the planned timing of the subsequent dosing (ie, extends until 7 days after the dose administration). For the 1st full dose, it extends up to 7 days past drug administration. Appendix 9 provides a comparison of the DDS considerations and a template for the reporting of DLT rates.

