## **Table 29 Template for Describing DLT Rates**

DL Cohort (Dosing Sequences)	Number FAS	Number DLT Evaluable	Number DLTs	DLT Rate
$a/b/c^*$ mg				
a/b/c/d* mg				
$b/c/d^*$ mg				
Supplementary DLT Rates for Period-Specific Dose Levels		I		
1st dose: a mg				
1st dose: b mg				
2 nd dose: b mg				
2 nd dose: c mg				
3 rd dose: c mg				
3 rd dose: d mg				
4 th dose: d mg				

\* prime/lower intermediate (/higher intermediate)/full dose numbered as: 1 st dose/2nd dose/3rd dose/3rd dose/3rd dose/3rd dose/4th dose.

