1.2 Timing of statistical analyses

Upon review and evaluation of the overall safety profile and safety signals of GEN1044 on 29 September 2021, Genmab Safety Committee classified pneumonitis as an important identified risk for GEN1044. Given this, further enrollment was stopped into GCT1044-01.

GEN1044 was tested in with a prime dose, followed by up to one intermediate dose, and then full doses until treatment discontinuation. The data will be summarized by the cohorts presented in Table 1.

		1 st Intermediate	2 nd Intermediate	
	Priming Dose	Dose	Dose / Full Dose	Full dose
Cohort	(C1D1)	(C1D8)	(C1D15)	(C2D1)
0.3/3/3 mg	0.3	3	3	3
1/5/5 mg	1	5	5	5
1/3/10 mg	1	3	10	10
1/3/30 mg	1	3	30	30
1/5/30 mg	1	5	30	30
1/10/30 mg	1	10	30	30
1/5/30/37.5 mg*	1	5	(30)	(37.5)
1/5/45 mg**	1	5	45	45
1/3/60 mg	1	3	60	60

Table 1: Dose Escalation Cohorts

2 Modification History

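### Protocol Sections 4.2 and 4.2.1.1 give conflicting limits for parallel cohorts when the parallel full dose equals the full dose under investigation (minor)

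*Protocol*

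**What the plan says.** Two places in protocol Version 4.0 set the limit for parallel cohorts in the Dose Escalation part.

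- **Section 4.2** allows a parallel cohort "provided the full-dose level of the parallel cohort has already been safety-cleared by the SC and does not equal or surpass the full-dose level" of the DL cohort being investigated. This is two conditions: prior SC clearance, and a full dose strictly below the one under investigation.
- **Section 4.2.1.1, Parallel Cohort(s) for Clinical Confirmation,** allows up to 7 more subjects, for a maximum DL cohort size of 10, at "full-dose levels that are considered safe for such allocation (dose levels at or below the currently investigated full dose" (the parenthesis ends there). Equality is included.

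Two further sentences bear on the same question. In Section 4.2, the 24-hour gap between subjects "will not apply to backfilling cohorts enrolling subjects to be exposed to previously safety-cleared full dose levels". In Section 4.2.1.1, the sentence after the parenthesis allows new priming or intermediate doses in a parallel cohort "provided its full-dose level does not exceed the most recent safety-cleared full-dose level".

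The SAP says nothing about parallel cohorts. It does record, after the SC classified pneumonitis as an important identified risk: "Given this, further enrollment was stopped into GCT1044-01".

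**The concern.** The clause in Section 4.2.1.1 permits dosing that Section 4.2 forbids. Someone working from Section 4.2.1.1 alone could treat the full dose under investigation as open for up to 7 parallel subjects while the escalation subjects at that dose are still in their DLT window. That window is 21 days with one intermediate dose and 28 days with two. The 24-hour stagger is aimed at acute signals and does not cover it.

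This is a first-in-human trial of a CD3 bispecific, and the design relies on assessing each new full dose in a small cohort before more subjects receive it. At stake is whether extra subjects may receive a full dose before that assessment is complete.

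**Working it through.** **Reproducing the plan's figure.** Section 4.2 gives 3 subjects per cohort once the single-subject phase has ended. Section 4.2.1.1 adds up to 7. 3 + 7 = 10, which matches the stated maximum DL cohort size.

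**The two rules, case by case.** A DL cohort is a dosing sequence (Table 29 heads its rows "DL Cohort (Dosing Sequences"), so two DL cohorts can share a full dose. The equality case therefore has two forms.

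| Parallel full dose | Section 4.2 | Section 4.2.1.1, parenthesis | Section 4.2.1.1, next sentence (new priming/intermediate doses) |
|---|---|---|---|
| Below the one under investigation, SC-cleared | allowed | allowed | allowed, up to the most recent cleared full dose |
| Equal, not yet cleared | forbidden (fails both conditions) | allowed | forbidden |
| Equal, already cleared under another sequence | forbidden (fails the second condition only) | allowed | allowed |
| Above | forbidden | forbidden | forbidden if uncleared |

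**Size of the conflict.** Parallel subjects allowed at the full dose under investigation: 0 under Section 4.2, up to 7 under the parenthesis. Doses strictly below it are treated alike, except that Section 4.2 states the clearance requirement outright.

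**Does other text settle it?**

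1. The stagger exemption and the sentence after the parenthesis both speak of cleared full doses. They support Section 4.2's first condition. Neither mentions the second, and the third row shows that the sentence after the parenthesis itself allows equality with a cleared dose.
2. Section 4.2.2 holds back escalation to the next level until the current DL cohort has passed its DLT period. It does not restrict parallel allocation at the current level.
3. The requirement in Section 4.2.1.1 that the dose be considered safe does not resolve the conflict, because the parenthesis glosses that phrase to include the dose under investigation. Reading SC clearance into it would leave Section 4.2's bar on equality still contradicted.

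**The case against.** The strongest reply is that the text could hardly mislead in practice. Under Section 6.1.2, escalation slots are assigned manually by the sponsor or its CRO, and a site needs approval before it starts screening. Under Sections 4.2 and 10.10, the Dose Escalation Committee (DEC) recommends and the SC decides. Section 4.2.1.1 only permits parallel allocation, so following the stricter Section 4.2 satisfies both. All of this stands and is the main reason the point is minor. It does not remove the conflict, because the committees themselves have two written limits and nothing says which one governs.

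A second reply is that SC clearance is what matters for safety, and that barring equality is needlessly strict where the full dose is already cleared and only the priming or intermediate dose is new. That is a coherent alternative rule, and the corroborating sentences are compatible with it. It would, however, require amending Section 4.2, which currently bars equality in plain terms.

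A reader might also infer that the looser limit was used, because SAP Table 1 lists three sequences with a 30 mg full dose (1/3/30, 1/5/30 and 1/10/30 mg). The table gives no opening dates and does not say whether any of them ran in parallel, so it is not evidence either way.

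**Conclusion.** The inconsistency is real and confined to one case: a parallel full dose equal to the full dose under investigation, where the permitted number is 0 by one section and up to 7 by the other. The conclusion rests on the wording of current Version 4.0 text and on no assumption about toxicity or accrual.

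Two stronger conclusions are not supported. The first is that the rest of the protocol confirms Section 4.2 in full; it confirms the clearance condition only. The second is that subjects were exposed to an uncleared full dose, or that a number of excess DLTs can be attached to the clause. The documents do not show that anyone was dosed under the looser limit, and the condition that the dose be considered safe, together with committee control, makes a worst-case count uninformative. With enrolment stopped, no further subject can be affected. Severity: minor.

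**What to change.** In Section 4.2.1.1, replace the parenthesis with Section 4.2's limit: full-dose levels already cleared by the SC and below the full dose in the DL cohort under investigation. Make the next sentence, on new priming or intermediate doses, subject to the same limit. Changing the parenthesis alone would leave the already-cleared equality case in conflict with Section 4.2.

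The change is to wording only and adds no subjects or procedures. Its cost is slightly less flexibility. Backfill at the current full dose would wait until that dose is cleared and a higher full dose is under investigation. A new priming or intermediate sequence could not run in parallel with another sequence at the same full dose. Since enrolment has stopped, the practical value is a consistent record and a corrected clause if this text is reused.

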## 4.2.2 Other Dose Escalation/De-Escalation Procedures

The following provides a description of the procedures not directly associated with the BOIN as such, but that will impact subject accrual and provisions for dose escalation/de-escalation decisions.

- 1. After completion of the first full dosing of each DL cohort, based on the safety data and the BOIN, the sponsor SC will decide on the dose-level for the next cohort of subjects. Escalation to the next dose-level will not occur until all subjects needed for a specific DL cohort have passed the Cycle 1/DLT evaluation period.
- 2. The Dose Escalation part will be assessed in dose-level cohorts (DL cohorts); initially this will be in done in single-subject cohorts until the trigger point (see Section 4.2) is passed.
  - A single-subject DL cohort may be optionally expanded with up to 2 additional subjects for the purpose of obtaining additional safety, PK, pharmacodynamic, and biomarker data (ie, for a total of 3 subjects in that cohort).
- 3. A subject will be considered as evaluable for dose determination if they experience a DLT or meet the minimum treatment and safety evaluation requirements for the first cycle (refer to Section 7.1).

After completion of the DLT period for each DL cohort, the DEC and sponsor SC will review the data from the DLT period to propose the actual next dose level. Data to be reviewed will include but not be limited to all relevant safety, clinical, PK, biomarker data, and the next dose as suggested by the BOIN strategies.

The RP2D to be used for the Expansion part will be determined at the end of the Dose Escalation part by the DEC and sponsor SC, based on a review of the totality of data, including but not limited to efficacy, safety (including DLTs, AEs, safety laboratory values, and observations made after the end of the DLT evaluation period), biomarker and PK data, and dosing information.

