#### 7 DOSE MODIFICATIONS AND SAFETY MANAGEMENT GUIDELINES

# 7.1 **Dose-Limiting Toxicity**

The DLT evaluation period is defined as the period from the start of the first GEN1044 administration on C1D1 of the Dose Escalation part of the trial until 7 days after the first full dose. As described in Section 4.1, if a subject receives the priming dose on C1D1, one intermediate dose on C1D8, and the full dose starting on C1D15, the DLT period will be the first 21 days of Cycle 1 (Cycle 1 days 1 through 21). If a subject receives the priming dose on C1D1, the first intermediate dose on C1D8, the second intermediate dose on C1D15, and the first full dose on C2D1, the DLT period will be Cycle 1 up to and including C2D7 (ie, a total of 28 days). The DLT evaluation period may be adjusted for potential GEN1044 treatment delay as described in Section 11.1.7.

National Cancer Institute (NCI) Common Terminology Criteria for Adverse Events (CTCAE) v5.0 (NCI-CTCAE, 2017) will be used to assess toxicities/AEs, except for CRS and immune effector cell-associated neurotoxicity syndrome (ICANS) (see Section 10.4.1 and Section 10.4.2, respectively).

A DEC is set up for the study. The DEC will review data from each DL cohort and make a decision regarding dose escalation. That decision of the DEC has to be confirmed by the sponsor SC. The DMC will review data on a quarterly basis.

Events to be collected and assessed by the DMC for DLTs include: SAEs; AESIs where applicable; and clinically significant abnormal laboratory values (that are not already covered by a separate AE term).

The occurrence of any of the toxicities outlined in this section will be considered a DLT if assessed by the investigator to be at least possibly related to GEN1044. AEs clearly not related to the trial treatment (GEN1044) such as disease progression, environmental factors, unrelated trauma, etc, should not be considered a toxicity event.

The following will qualify for a DLT:

- ≥ Grade 3 CRS, graded according to American Society for Transplantation and Cellular Therapy (ASTCT) criteria (Lee et al., 2019) (see Section 10.4.1, Table 16).
- \geq Grade 3 ICANS, graded according to the criteria specified in Table 17, Section 10.4.2.
- Any Grade 3 or 4 non-hematologic toxicity except for:
  - Grade ≥ 3 nausea/vomiting or diarrhea <72 hours with adequate anti-emetic and other supportive care
  - Grade  $\geq$  3 fatigue  $\leq$ 1 week

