  - Grade ≥ 3 electrolyte abnormality that lasts <72 hours, unless the patient has clinical symptoms, in which case all grade ≥3 electrolyte abnormality regardless of duration should count as a DLT
  - Grade ≥ 3 amylase or lipase elevation NOT associated with symptoms or clinical manifestations of pancreatitis does not need to be counted as a DLT
  - o Laboratory abnormalities are excluded except for below:
    - Clinically significant medical intervention is required to treat the subject, OR
    - The abnormality leads to hospitalization, OR
    - The abnormality persists for >1 week, OR
    - The abnormality results in a drug-induced liver injury (DILI)
- Any Grade 3 or 4 hematologic toxicity, except for:

Version: 4.0

- Grade  $\geq$  3 lymphocytopenia lasting  $\leq$ 72 hours
- Grade 3 thrombocytopenia not associated with impaired hemostasis, clinically significant bleeding or required platelet transfusion therapy
- Grade  $\geq$  3 ANC lasting <7 days and without fever
- Grade 3 or grade 4 febrile neutropenia:
  - o Grade 3 is defined as absolute neutrophil count (ANC) <1000/mm³ with a single temperature of >38.3°C (101°F) or a sustained temperature of ≥38°C (100.4°F) for more than 1 hour.
  - o Grade 4 is defined as ANC <500/mm³ with a single temperature of >38.3°C (101°F) or a sustained temperature of ≥38°C (100.4°F) for more than 1 hour, with life-threatening consequences and urgent intervention indicated.
- Liver toxicity as defined by Hy's Law (FDA-Guidance, 2009) below:
  - o Aminotransferase (ALT and/or AST) >3×ULN.
  - o Total bilirubin >2×ULN, without initial findings of cholestasis (elevated serum alkaline phosphatase).
  - No other reason can be found to explain the combination of increased ALT/AST and total bilirubin.
- Any treatment-related toxicity that causes the subject to discontinue treatment during Cycle 1.
- Any grade 5 toxicity.

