## **Appendix 8 Recommended ICANS Management**

Source: (Garcia Borrega et al., 2019; Lee et al., 2019)

<sup>2 Borrega Garcia et al., 2019.

Version: 4.0

## Appendix 9 Description of DLT Rates After Protocol Amendment 3

Table 28 Dose-Determining Analysis Sets Comparison

DLT Consideration	Number FAS	Number DLT Evaluable	DLT Period	Comment
DL cohort	All those with at least 1 dose (ie, prime dose) administered	All those who meet the exposure criteria for the DL cohort, or experience a DLT during the DLT period	Up to 7 days past 1 st full dose administration	Regardless of what individual dose that the DLT could be associated with, the DLT is attributed to DL cohort as such
Period-specific DLT rates	All those administered the period-specific dose	All those administered the period-specific dose in a timely fashion	Up to 7 days past dose administration	

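### Protocol 4.2.1.2 admits priming-dose CRS to the mBOIN only at grade ≥3, but 7.1 makes grade 2 CRS that ends treatment in Cycle 1 a DLT; read literally, 1/3 'remain' becomes 0/3 'escalate'

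*Protocol*

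**What the plan says.** Protocol 4.2.1.2 covers grade ≥2 CRS in the first 7 days of Cycle 1. The incidence at the priming dose goes to the DEC "as descriptive statistics to determine the feasibility of the priming dose level from a CRS management perspective". The section then ends: "The CRS event will only be used in the mBOIN model if it is a grade" 3 or higher.

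Protocol 7.1 defines the DLTs. A listed toxicity "will be considered a DLT if assessed by the investigator to be at least possibly related to GEN1044". CRS of grade 3 or higher is one item on the list. A later, separate item is "Any treatment-related toxicity that causes the subject to discontinue treatment during Cycle 1". That item has no grade limit and no exception for CRS.

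Three other places govern how a DLT is counted:

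- Protocol 4.2.2, item 3: "A subject will be considered as evaluable for dose determination if they experience a DLT", or if the minimum treatment and safety requirements are met. Section 11.1.7 and Appendix 9, Table 28, say the same in substance.
- Appendix 9, Table 28: "Regardless of what individual dose that the DLT could be associated with, the DLT is attributed to DL cohort as such".
- Protocol 11.1.7: "DLTs occurring beyond the DLT period will be presented, but not contribute to the DLT rates for the DL cohort per mBOIN". For DLTs, this timing rule is the only exclusion from the cohort mBOIN rate that the section states.

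The escalation decision is read from Table 11, which is indexed by "Total Number of DLT Evaluable Subjects Treated on a DL Cohort" and by the number of DLTs in that cohort.

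**The concern.** The two sections give different answers for one defined event: grade 2 CRS after the priming dose that leads to discontinuation in Cycle 1. Under 7.1 it is a DLT. It falls inside the DLT period, so the timing exclusion in 11.1.7 does not apply, and Table 28 assigns it to the DL cohort. Under 4.2.1.2, because it is below grade 3, it may not be used in the model. Neither section refers to the other, and no other text reconciles them.

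At stake is the input to the escalation rule. A subject who could not continue because of a drug-related toxicity would be counted as treated and evaluable but without a DLT. The recommendation could then be to escalate where the protocol's own DLT definition says to stay at the dose.

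**Working it through.** **Inputs.** Protocol 4.2.1 gives a target DLT rate φ = 0.30, with φ₁ = 0.6φ = 0.18 and φ₂ = 1.4φ = 0.42, and stated thresholds of 24% and 36%. The decisions come from Table 11. The handling of small cohorts comes from 4.2.1.1.

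**Step 1: reproduce the plan's thresholds.**

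- λ₁ = ln[(1−φ₁)/(1−φ)] / ln[φ(1−φ₁)/(φ₁(1−φ))] = ln(0.82/0.70) / ln(0.246/0.126) = 0.2365
- λ₂ = ln[(1−φ)/(1−φ₂)] / ln[φ₂(1−φ)/(φ(1−φ₂))] = ln(0.70/0.58) / ln(0.294/0.174) = 0.3585

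These round to the stated 24% and 36%. With escalate if x/n ≤ λ₁, de-escalate if x/n ≥ λ₂, and terminate if x/(n+3) ≥ λ₂, every cell of Table 11 for n = 3 to 9 is reproduced.

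**Step 2: leave one DLT out, n unchanged.** This is the literal result. Section 7.1 makes the event a DLT, so the subject is evaluable and stays in n; 4.2.1.2 keeps the event out of x.

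| n | 'Remain' under 7.1 | Becomes 'escalate' | 'De-escalate' under 7.1 | Becomes 'remain' |
|---|---|---|---|---|
| 3 | 1/3 (33%) | 0/3 | 2/3 | 1/3 |
| 4 | 1/4 (25%) | 0/4 | 2/4 | 1/4 |
| 6 | 2/6 (33%) | 1/6 (17%) | 3/6 | 2/6 |
| 7 | 2/7 (29%) | 1/7 (14%) | 3/7 | 2/7 |
| 8 | 2/8 (25%) | 1/8 (13%) | 3/8 | 2/8 |
| 9 | 3/9 (33%) | 2/9 (22%) | 4/9 | 3/9 |

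At each of these sizes 'remain' and 'de-escalate' cover exactly one DLT count, so a single lost event always moves the recommendation from those cells. The case n = 5 is left out because 4.2.1.1 brings it up to 6. Lowering x with n fixed can never make the recommendation more cautious.

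**Step 3: the alternative denominator.** Suppose 4.2.1.2 were taken to mean that the event is not a DLT at all. A subject stopped after priming then fails the exposure criterion in 11.1.7 and leaves the denominator.

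- 1/3 becomes 0/2, which 4.2.1.1 also treats as 'escalate', provided neither remaining subject had a grade ≥2 AE in the first 7 days or a DLT.
- 1/4, 2/7 and 2/8 become 0/3, 1/6 and 1/7, all 'escalate'.
- 2/6 becomes 1/5, which 4.2.1.1 would bring up to 6.
- 3/9 becomes 2/8, still 'remain'.

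So at three subjects the shift to 'escalate' does not depend on which denominator is used, apart from that proviso.

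**Step 4: illustration of frequency (assumed rates).** The documents give no rate for grade 2 CRS leading to discontinuation. Assume other DLTs in 20% of subjects and, in different subjects, this event in 2% to 10%. The chance that a three-subject cohort yields no counted DLT, and so 'escalate', is (1 − 0.20 − 0.02)³ = 47.5% down to (1 − 0.20 − 0.10)³ = 34.3% under 7.1. It is (1 − 0.20)³ = 51.2% under 4.2.1.2 read literally. The table in step 2 does not rest on these assumptions.

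**The case against.** The strongest reply is that the two sections were never meant to conflict. Section 4.2.1.2 describes grade ≥2 CRS, and grade ≥2 AEs already trigger expansion of a single-subject cohort in 4.2. The sentence can be read as saying that grade 2 CRS as such is not a model event, in line with the CRS item in 7.1. A discontinuation would then count under its own criterion. All the counting rules (Table 11, 11.1.7, 11.5.2 and Table 28) work on DLTs, and nothing describes a step that subtracts a DLT before the model is applied. This is probably the intent. It does not cure the text: the sentence says 'only', it concerns the CRS event rather than the CRS criterion, and it has no reference to 7.1.

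The 0/3 count also applies 7.1 to the denominator and sets it aside for the numerator. That is a fair description of the literal reading, but with three subjects the alternative 0/2 also gives 'escalate', subject to the proviso in step 3.

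The remaining objections stand and limit the impact. Section 7.2.1 does not require stopping for grade 2 CRS, so the case needs a discretionary stop. The DEC receives the priming CRS incidence regardless, the mBOIN output is a recommendation, and the Safety Committee makes the final decision. SAP 1.2 records that enrolment was stopped, and SAP 9.1 summarises DLTs by preferred term with no mBOIN re-analysis.

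**Conclusion.** The concern holds. As written, 4.2.1.2 excludes from the escalation model an event that 7.1 defines as a DLT. One such event changes the Table 11 recommendation by one step in the less cautious direction at twelve cells: six from 'remain' to 'escalate' and six from 'de-escalate' to 'remain'. The result depends on reading 'only' literally and on the subject staying evaluable, which 4.2.2, 11.1.7 and Table 28 support. It does not depend on any event rate.

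The severity is minor. The event is likely uncommon, the intended meaning is probably harmless, the committees can depart from the recommendation, and no further escalation decision in this trial will use the sentence.

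**What to change.** Replace the last sentence of Protocol 4.2.1.2 with: *A CRS event enters the mBOIN if it meets any DLT criterion in Section 7.1 (grade ≥3, or any grade that causes treatment discontinuation during Cycle 1).* The definitions of the dose-determining set need no change for this point.

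The cost is one sentence, with no new data and no new analysis. Because enrolment has stopped, the practical equivalent is a line in the clinical study report stating which rule was applied to CRS events when the mBOIN recommendations were formed. The current wording should not be carried into later protocols.
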